8.3.3 Suspected Unexpected Serious Adverse Reactions (SUSAR)

A SUSAR is any SAE where a causal relationship with the study product is at least reasonably possible but is not listed in the Investigator’s Brochure (IB), Package Insert, and/or Summary of Product Characteristics.

8.3.4 Classification of an Adverse Event

The determination of seriousness, severity and causality will be made by an on-site investigator who is qualified (licensed) to diagnose AE information, provide a medical evaluation of AEs and classify AEs based upon medical judgment. This includes, but is not limited to, physicians, physician assistants and nurse practitioners.

8.3.4.1 Severity of Adverse Events

All AEs and SAEs will be assessed for severity, according to the toxicity grading scales in the FDA “Toxicity Grading Scale for Healthy Adult and Adolescent Volunteers Enrolled in Preventive Vaccine Clinical Trials”.

For AEs not included in the protocol-defined grading system, the following guidelines will be used to describe severity.

- **Mild (Grade 1):** Events that are usually transient and may require only minimal or no treatment or therapeutic intervention and generally do not interfere with the subject’s usual activities of daily living.
- **Moderate (Grade 2):** Events that are usually alleviated with additional specific therapeutic intervention. The event interferes with usual activities of daily living, causing discomfort but poses no significant or permanent risk of harm to the research subject.

- **Severe (Grade 3):** Events interrupt usual activities of daily living, or significantly affects clinical status, or may require intensive therapeutic intervention. Severe events are usually incapacitating.

AEs characterized as intermittent require documentation of onset and duration of each episode. The start and stop date of each reported AE will be recorded on the appropriate DCF. Changes in the severity of an AE will be documented to allow an assessment of the duration of the event at each level of intensity.

8.3.4.2 Relationship to Study Intervention

For each reported adverse reaction, the participating site PI or qualified designee must assess the relationship of the event to the study product using the following guidelines:

- **Related** – The AE is known to occur with the study intervention, there is a reasonable possibility that the study intervention caused the AE, or there is a temporal relationship between the study intervention and event. Reasonable possibility means that there is evidence to suggest a causal relationship between the study intervention and the AE.
- **Not Related** – There is not a reasonable possibility that the administration of the study intervention caused the event, there is no temporal relationship between the study intervention and event onset, or an alternate etiology has been established.

8.3.5 Time Period and Frequency for Event Assessment and Follow-Up

For this study:

- solicited AEs will be collected for 7 days post each vaccination.
- unsolicited AEs will be collected until 28 days post last vaccination
- SAEs, Protocol Specified AESIs, MAAEs, and NOCMCs will be collected from Day 1 through the end of the study.

8.3.6 Adverse Event Reporting

8.3.6.1 Investigators Reporting of AEs

Information on all AEs should be recorded on the appropriate DCF. All clearly related signs, symptoms and results of diagnostic procedures performed because of an AE should be grouped together and recorded as a single diagnosis. If the AE is a clinical laboratory abnormality that is part of a clinical condition or syndrome, it should be recorded as the syndrome or diagnosis rather than the individual clinical laboratory abnormality. Each AE will also be described in terms of duration (start and stop date), severity, association with the study product, action(s) taken, and outcome.

8.3.7 Serious Adverse Event Reporting

8.3.7.1 Investigators Reporting of SAEs

Any AE that meets a protocol-defined criterion as an SAE must be submitted immediately (within 24 hours of site awareness) on an SAE form to the DMID Pharmacovigilance Group, at the following address:

DMID Pharmacovigilance Group
Clinical Research Operations and Management Support (CROMS)
[name]
[name]
SAE Hot Line: [name] (US) or [name] (outside US)
SAE [contact] (US) or [name] (outside US)
SAE Email Address: [contact]

In addition to the SAE form, select SAE data fields must also be entered into the SDCC system. Refer to the protocol-specific MOP for details regarding this procedure.

Other supporting documentation of the event may be requested by the DMID Pharmacovigilance Group and should be provided as soon as possible. The DMID Medical Monitor will review and assess the SAE for regulatory reporting and potential impact on study subject safety and protocol conduct.

At any time after completion of the study, if the participating site PI or appropriate sub-investigator becomes aware of an SAE that is suspected to be related to study product, the participating site PI or appropriate sub-investigator will report the event to the DMID Pharmacovigilance Group.

8.3.7.2 Regulatory Reporting of SAEs

Following notification from the participating site PI or appropriate sub-investigator, DMID, as the IND sponsor, will report any SUSAR in an IND safety report to the FDA and will notify all participating site PIs (i.e., all PIs to whom the sponsor is providing drug under its IND(s) or under any PI's IND(s)) of potential serious risks from clinical studies or any other source, as soon as possible. DMID will report to the FDA any unexpected fatal or life-threatening suspected adverse reaction as soon as possible, but in no case later than 7 calendar days after the sponsor's initial receipt of the information. If the event is not fatal or life-threatening, the IND safety report will be submitted within 15 calendar days after the sponsor determines that the information qualifies for reporting as specified in 21 CFR Part 312.32. Relevant follow-up information to an IND safety report will be submitted as soon as the information is available. Upon request from FDA, DMID will submit to the FDA any additional data or information that the agency deems necessary, as soon as possible, but in no case later than 15 calendar days after receiving the request.

SAEs that are not SUSARs will be reported to the FDA at least annually in a summary format which includes all SAEs.

8.3.8 Reporting Events to Subjects

Subjects will be informed of any AEs or SAEs that occur as part of their participation in this trial.

8.3.9 Adverse Events of Special Interest (AESIs)

Adverse Events of Special Interest (AESIs) represent any events for which additional data (besides the standard AE data) are desired. An adverse event of special interest (serious or nonserious) is one of scientific and medical concern specific to the sponsor's product or

program, for which ongoing monitoring and rapid communication by the investigator to the sponsor is required. Such an event may require further investigation in order to characterize and understand it. Depending on the nature of the event, rapid communication by the trial sponsor to other parties (e.g., regulators) may also be required. These may be at the request of the regulatory agency, industry partner or DMID, and driven by a regulatory requirement, or known or potential risk from the product or class. Non-structured data similar to SAEs will be collected for AESIs. AESIs encompass the following terms:

- Protocol Specified AESIs: See [Section 12](#), Appendix A.
 - All suspected cases of anaphylaxis should be recorded. For reporting purposes, a participant who displays signs/symptoms consistent with anaphylaxis should be reported as a potential case of anaphylaxis.
 - All suspected cases of myocarditis or pericarditis should be recorded. For reporting purposes, a participant who displays signs/symptoms consistent with myocarditis or pericarditis should be reported as a potential case of myocarditis or pericarditis.
- NOCMCs – defined as any new ICD diagnosis (per current International Statistical Classification of Diseases and Related Health Problems) that is applied to the subject during the course of the study, after receipt of the study agent, that is expected to continue for at least 3 months and requires continued health care intervention.
- MAAEs – defined as a hospitalization, emergency room visit or an otherwise unscheduled visit to or from medical personnel for any reason; and considered related to study product.

All AESIs are assessed, recorded, and followed as described above under AEs. AESIs that meet SAE criteria will be reported on an SAE form within 24 hours to the DMID Pharmacovigilance Group, at the following address:

DMID Pharmacovigilance Group
Clinical Research Operations and Management Support (CROMS)
[name]
[name]
SAE Hot Line: [name] (US) or [name] (outside US)
SAE [contact] (US) or [name] (outside US)
SAE Email Address: [contact]

In addition, for documentation and medical assessment purposes AESIs that do not meet SAE criteria will also be reported on an SAE form within the period for AE reporting to the DMID Pharmacovigilance Group; however, the narrative will indicate that the AESI did not meet SAE criteria.

8.3.10 Reporting of Pregnancy

Pregnancy is not an AE. However, any pregnancy that occurs during study participation (through the end of the study) should be reported to the sponsor on the appropriate DCF. Pregnancy should be followed to outcome.

8.4 Unanticipated Problems

8.4.1 Definition of Unanticipated Problems (UPs)

The Department of Health and Human Services (DHHS) OHRP considers unanticipated problems involving risks to subjects or others to include, in general, any incident, experience, or outcome that meets all of the following criteria:

- Unexpected in terms of nature, severity, or frequency given (a) the research procedures that are described in the protocol-related documents, such as the IRB-approved research protocol and informed consent document; and (b) the characteristics of the subject population being studied;
- Related or possibly related to participation in the research (“possibly related” means there is a reasonable possibility that the incident, experience, or outcome may have been caused by the procedures involved in the research); and
- Suggests that the research places subjects or others at a greater risk of harm (including physical, psychological, economic, or social harm) than was previously known or recognized.

8.4.2 Unanticipated Problem Reporting

To satisfy the requirement for prompt reporting, UPs will be reported using the following timeline:

- UPs that are SAEs will be reported to the IRB and to the SDCC/study sponsor within 24 hours of the participating site PI or appropriate sub-investigator becoming aware of the event per the above-described SAE reporting process.
- UPs that are SAEs will be collected from Day 1 through the end of the study.
- Any other UP will be reported to the IRB and to the SDCC/study sponsor within 3 days of the participating site PI or appropriate sub-investigator becoming aware of the problem.
- UPs that are not SAEs will be collected from Day 1 through 28 days after last vaccination.

8.4.3 Reporting Unanticipated Problems to Subjects

Subjects will be informed of any UPs that occur as part of their participation in this trial.

9. STATISTICAL CONSIDERATIONS

9.1 Statistical Hypotheses

This is a phase 1, open-label, randomized clinical trial and is not designed to test a specific hypothesis. Rather, it is intended to obtain preliminary estimates in healthy adults of the safety, reactogenicity, and immunogenicity of mRNA-1273.351 alone and in combination with mRNA-1273.

9.2 Sample Size Determination

Rare AEs are not demonstrable in a clinical study of this size; however, the probabilities of observing one or more AEs given various true event rates are presented in Table 12. With the assumption that all enrolled subjects will likely complete immunizations and safety visits in this relatively short duration study, the following statistical considerations apply. With approximately 30 subjects in each arm (Arms 1A and 1B), the chance of observing at least one AE of probability 10% or more is approximately 96%. Therefore, if no AEs of a given type occur in a Cohort 1 Arm, we can be relatively confident that they will occur in fewer than 10% of people once the vaccine is implemented. With approximately 60 subjects across these two Arms (1A and 1B), the chance of observing at least one AE of probability 5% or more is at least 95%. Therefore, if no AEs of a given type occur across Cohort 1, we can be very confident that any combination independent event will occur in fewer than 5% of people once the vaccine is implemented as a boost.

With 15 subjects in Arms 2A and 2B, the chance of observing at least one AE of probability 20% or more is approximately 97%. Therefore, if no AEs of a given type occur in Arms 2A or 2B, we can be relatively confident that they will occur in fewer than 20% of people once the vaccine is implemented. With 20 subjects in each arm (Arms 2C-2H), the chance of observing at least one AE of probability 20% or more is approximately 99%. Therefore, if no AEs of a given type occur in Arms 2C-2H, we can be relatively confident that they will occur in fewer than 20% of people once the vaccine is implemented. With approximately 150 subjects across these eight Arms (2A-2H), the chance of observing at least one AE of probability 3% or more is at least 99%. Therefore, if no AEs of a given type occur across Cohort 2, we can be very confident that any dosage/combination independent event will occur in fewer than 3% of people once the vaccine is implemented.

Table 12: Probability of Observing an Adverse Event for Various Event Rates

Cohort 1					
N	“True” Event Rate	Probability of Observation (%)	N	“True” Event Rate	Probability of Observation (%)
30	0.1%	3.0	60	0.1%	5.8
	0.5%	14.0		0.5%	26.0
	1.0%	26.0		1.0%	45.3
	2.0%	45.5		2.0%	70.2
	3.0%	59.9		3.0%	83.9
	4.0%	70.6		4.0%	91.4
	5.0%	78.5		5.0%	95.4
	10.0%	95.8		10.0%	99.8
	15.0%	99.2		15.0%	>99.9
	20.0%	99.9		20.0%	>99.9
Cohort 2					
N	“True” Event Rate	Probability of Observation (%)	N	“True” Event Rate	Probability of Observation (%)
15	0.1%	1.5	20	0.1%	2.0
	0.5%	7.2		0.5%	9.5
	1.0%	14.0		1.0%	18.2
	2.0%	26.1		2.0%	33.2
	3.0%	36.7		3.0%	45.6
	4.0%	45.8		4.0%	55.8
	5.0%	53.7		5.0%	64.2
	10.0%	79.4		10.0%	87.8
	15.0%	91.3		15.0%	96.1
	20.0%	96.5		20.0%	98.8
N = 150					

9.3 Populations for Analyses

The Safety Analysis population for the study includes all subjects who received one dose of study vaccine. Analyses for the safety population will include safety reported through the end of the study. The modified intent-to-treat (mITT) population includes all subjects who received at least one dose of vaccine and contributed both pre- and at least one post-vaccination venous blood sample for immunogenicity testing for which valid results were reported.

In the final analysis, protocol deviations will be reviewed to determine which protocol deviations may affect the analysis. The per protocol (PP) population will then be defined – and this includes all subjects in the mITT subset with the following exclusions:

- Data from all available visits for subjects found to be ineligible at baseline.
- Data from all visits subsequent to the protocol deviations that are considered to affect the science.
- Data from any visit that occurs substantially out of window.

9.4 Statistical Analyses

Interim analyses of safety, reactogenicity, and immunologic response data will be done, as needed.

The final analysis will be performed after the final data lock and clinical study report (CSR) completed when all primary safety endpoint data and all secondary immunogenicity endpoint data are available and received by the SDCC. Any available data from the exploratory immunogenicity endpoints may also be included in the CSR. Remaining exploratory immunogenicity endpoint data may be included in an addendum to the CSR, publication of manuscript(s), or other report(s). Abbreviated analysis plans that describe planned analyses to facilitate dissemination of study data for public health reasons, including manuscript publication(s), will be developed by the SDCC. A full statistical analysis plan (SAP) will be developed by the SDCC and finalized prior to the primary data lock.

9.4.1 General Approach

Unless otherwise noted in the SAP, continuous variables will be summarized using the following descriptive statistics: n (non-missing sample size), mean, standard deviation, median, maximum and minimum. The frequency and percentages (based on the non-missing sample size) of observed levels will be reported for all categorical measures.

9.4.2 Analysis of the Primary Endpoint(s)

[Section 9.4.4](#) describes the analyses of Safety which is the primary endpoint of this protocol.

9.4.3 Analysis of the Secondary Endpoint(s)

Summaries and analysis of immunogenicity data will be presented for the mITT population. If there are protocol deviations which may affect the analysis, a per-protocol (PP) analysis may also be performed.

Seroconversion is defined as a 4-fold increase in antibody titer over baseline.

Seroconversion rates, GMFR and GMT for SARS-CoV-2 as measured by a range of assays measuring total Spike-specific IgG (ELISA-based) and function (neutralization, receptor binding domain (RBD) binding, or similar) will be calculated for all timepoints by arm and will be summarized graphically. Seroconversion rates, GMFR and GMT will be presented with their corresponding 95% CI estimates at each timepoint and overall peak GMT.

9.4.4 Safety Analyses

Summaries and analysis of safety data will be presented for the Safety Analysis Population.

Solicited AEs will be summarized by severity for each day post vaccination (Days 1-8) and as the maximum severity over all 8 days. Additionally, solicited AEs will be analyzed using standard techniques, such as exact confidence intervals (CI), to summarize the proportion of subjects reporting each symptom, any application site symptom, and any systemic symptom.

Unsolicited non-serious AEs will be collected from the time of first vaccination through 28 days after the last vaccination. Unsolicited AEs will be coded by MedDRA for preferred term and system organ class (SOC). SAEs, Protocol Specified AESIs, MAAEs, and NOCMCs will be collected from the time of first vaccination through the end of the study. The numbers of SAEs, Protocol Specified AESIs and MAAEs will be reported by detailed listings showing the event description, MedDRA preferred term and SOC, relevant dates (vaccinations and AEs), severity, relatedness, and outcome for each event. Non-serious unsolicited AEs will be summarized as number and percentage of subjects reporting at least one event in each MedDRA preferred term and SOC, cross tabulated by severity and relationship to study product. Additionally, the proportion of subjects and exact 95% CIs of AEs in aggregate and by MedDRA categories will be computed.

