3. OBJECTIVES AND ENDPOINTS

Table 6: Objectives and Endpoints (Outcome Measures)

OBJECTIVES	ENDPOINTS (OUTCOME MEASURES)
Primary	

To evaluate the safety and reactogenicity of mRNA-1273 and mRNA-1273.351 vaccines, in naïve and previously vaccinated individuals.	
Frequency and grade of each solicited local and systemic reactogenicity AE during a 7-day follow-up period post each vaccination.Frequency and grade of any unsolicited AEs during the 28-day follow-up period post each vaccination.Frequency of any SAEs, Protocol Specified AESIs, NOCMCs, and MAAEs

OBJECTIVES	ENDPOINTS (OUTCOME MEASURES)
	from the first vaccination through 12 months after the last vaccination.
Secondary	

To assess humoral immunogenicity of mRNA-1273 and mRNA-1273.351 vaccines, in naïve and previously vaccinated individuals.	
Response rate, and magnitude of SARS-CoV-2-specific antibody binding and neutralization titers in serum samples as assessed via a range of assays at all timepoints.
Exploratory	

To assess, in at least a subset of samples the innate immune response and B cell response following vaccination.	
Magnitude, phenotype, and percentage of innate immune cells and SARS-CoV-2 specific B cells, as measured by flow cytometry, and targeted B cell repertoire analysis at different timepoints post vaccination relative to baseline.

To assess, in at least a subset of samples, the SARS-CoV-2 S protein-specific T cell responses.	
Magnitude, phenotype, and percentage of cytokine producing S protein-specific T cells, as measured by flow cytometry at different timepoints post vaccination relative to baseline.

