8.3.1.2 Unsolicited Adverse Events

All AEs spontaneously reported by the subject and/or in response to an open question from study staff or revealed by observation, physical examination or other diagnostic procedures must be recorded on the appropriate DCF.

Unsolicited AEs of all severities will be reported from the time of study product administration through 28 days post last vaccination.

After 28 days post last vaccination through the end of study, only SAEs, Protocol Specified AESIs, MAAEs, and NOCMCs (as detailed in [Section 8.3.2](#)) will be reported as AEs.

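### A primary endpoint grades all unsolicited adverse events, but the only planned severity-by-relationship table leaves out the serious ones

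*Protocol*

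**What the plan says.** Table 6 in Section 3 of the protocol sets three primary safety endpoints. The one on unsolicited events reads "Frequency and grade of any unsolicited AEs during the 28-day follow-up period post each vaccination". It has no carve-out for serious events. A separate endpoint, running to 12 months after the last vaccination, is "Frequency of any SAEs, Protocol Specified AESIs, NOCMCs, and MAAEs"; it asks for frequency and does not mention grade.

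Section 8.3.1.2 collects unsolicited events on the same broad footing: "Unsolicited AEs of all severities will be reported from the time of study product administration through 28 days post last vaccination".

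Section 9.4.2 hands the primary analysis to Section 9.4.4, saying that it "describes the analyses of Safety which is the primary endpoint of this protocol". On unsolicited and serious events, Section 9.4.4 plans three displays:

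- A subject-level table: "Non-serious unsolicited AEs will be summarized as number and percentage of subjects reporting at least one event in each MedDRA preferred term and SOC", and this table is "cross tabulated by severity and relationship to study product".
- Listings: "The numbers of SAEs, Protocol Specified AESIs and MAAEs will be reported by detailed listings showing the event description". Each listed event also carries its coded term, dates, severity, relatedness and outcome.
- Proportions with intervals: "Additionally, the proportion of subjects and exact 95% CIs of AEs in aggregate and by MedDRA categories will be computed". This sentence is not limited to non-serious events, but it names neither grade nor relationship.

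**The concern.** The endpoint has two halves, frequency and grade, and both apply to any unsolicited event. The analysis delivers the grade half only for events that did not meet a seriousness criterion. Events therefore leave the grade table because of their outcome. Where that changes a count of subjects with at least one event, it can only lower it.

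The arms are small: 15 subjects in 2A and 2B, 20 in 2C to 2H, and about 30 in 1A and 1B. One subject can be the difference between an empty and a non-empty severe row. Section 9.2 reasons from zeros, inferring from the absence of a given type of event in an arm that its true rate is below 10% or 20%. A zero in the severity table that arises only because serious events were left out could be read in the same way. Section 9.4.6 lets the sponsor present primary endpoint results by arm while the study is running, so the table may be read apart from the listings.

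**Working it through.** No figure in the protocol is in dispute. The check is a comparison of texts, followed by a small illustration of size.

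**Step 1. Does unsolicited already mean non-serious here?** No. Section 8.3.1 divides adverse events into solicited and unsolicited by how they are elicited, not by seriousness. Section 8.3.1.2 covers every severity. Section 9.4.4 itself adds the word non-serious as a qualifier, which would be redundant if unsolicited events were non-serious by definition. A serious unsolicited event within 28 days therefore belongs to the Table 6 endpoint.

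**Step 2. Which planned display shows its grade?**

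| Display in Section 9.4.4 | Includes serious unsolicited events? | Subject-level count? | By grade? |
|---|---|---|---|
| Term and organ-class table | No | Yes | Yes |
| Listings of serious events | Yes | No, event by event | Grade shown per event, not summarised |
| Proportions with exact intervals | Not excluded | Yes | No |

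No row answers yes in all three columns. The endpoint needs all three.

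**Step 3. Are the data there?** Yes. Section 8.3.2 requires every serious event to be assessed for severity and relationship, as for any other adverse event. A combined table needs no new collection.

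**Step 4. How large can the difference be?** Let n be the arm size and x the number of subjects with at least one non-serious event in a given cell, such as Grade 3. Let s be the number of subjects who have a serious event in that cell and no non-serious event in it.

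- Planned table: x / n
- Endpoint as defined: (x + s) / n
- Difference: s / n

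The protocol gives no expected rate of serious events, so s is an assumption. With x = 0:

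| n | Planned table | s = 1 | s = 2 |
|---|---|---|---|
| 15 | 0/15 = 0% | 1/15 = 6.7% | 2/15 = 13.3% |
| 20 | 0/20 = 0% | 1/20 = 5.0% | 2/20 = 10.0% |
| 30 | 0/30 = 0% | 1/30 = 3.3% | 2/30 = 6.7% |

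If the subject with the serious event also has a non-serious event counted in the same cell, then s = 0 and nothing changes. No confidence intervals are attached to these cells because Section 9.4.4 plans none for the severity cross-tabulation.

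**The case against.** The strongest reply is that nothing is hidden. Every serious event is listed with its grade and causality, and at 15 to 30 subjects per arm a reader could rebuild the combined table by hand. For a single event, an individual listing is arguably the most visible display. Serious events also have their own primary endpoint, and separate displays for serious and non-serious events are a common layout. All of this stands and limits the weight of the point. It does not close the gap, because a listing is not a summary of frequency by grade and the endpoint on serious events does not ask for grade.

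A second reply is that the frequency half of the endpoint is met by the proportions with exact intervals. That is right; only the grade half is affected.

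A third is that Section 9.4.1 promises frequencies and percentages for all categorical measures, and that table layout belongs in the statistical analysis plan, which is not shown. The general line in Section 9.4.1 does not say which events are counted and does not override the specific restriction in Section 9.4.4. Nor has the protocol left the matter open: it fixes a rule that is narrower than its own endpoint.

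A reader might also infer more than the documents support:

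- *That serious events are mostly the higher-grade ones, so the table loses most severe events.* The protocol defines seriousness by outcome (Section 8.3.2) and grade by intensity (Section 8.3.4.1). It says nothing about how far they overlap, and non-serious Grade 3 events stay in the table.
- *That every serious event in the window lowers an arm's estimate.* The table counts subjects with at least one event, so the cell moves only under the condition in Step 4.
- *That safety oversight is weakened.* A vaccine-related serious event pauses the study under Section 7.1.1. The Grade 3 pausing rule there is not limited to non-serious events, and serious events go to the safety monitoring committee under Section 8.3.2.

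**Conclusion.** The mismatch is real and confined to the grade half of one primary endpoint. Table 6 asks for the grade of any unsolicited event; Section 9.4.4 cross-tabulates grade and relationship for non-serious ones only. As written, no planned summary gives the grade distribution over all unsolicited events, and a grade category can be understated when a subject's only event at that grade is serious.

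The illustrative size is 3.3 to 6.7 percentage points per such subject, depending on the arm. It assumes at least one such subject, and the protocol gives no rate from which to judge how likely that is. With no serious unsolicited event in the window, the planned and complete tables are identical.

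This is a minor to moderate reporting correction. The trial tests no hypothesis (Section 9.1), and nothing here bears on sample size, pausing rules or error rates.

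**What to change.** In Section 9.4.4, define the main table as all unsolicited adverse events, serious and non-serious, with onset within 28 days after a vaccination. Report it as the number and percentage of subjects by preferred term and system organ class, split by severity and relationship. Keep the non-serious table and the listings of serious events as supplementary displays.

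The cost is one change of wording and one rerun of a table already planned, using data already collected. Rates of severe events may look slightly less favourable in an arm where a serious event falls in the window.
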